## Background, Rationale and Goals

### 1. \* Describe the study's background and what is currently known from the scientific literature, including citations, or upload a citation list in document upload. Use lay language whenever possible.

All tobacco products, including electronic cigarettes (ECIGs) are now regulated by the FDA. FDA's "public health standard" requires consideration of how tobacco product regulation will influence risks and benefits to tobacco product users and non-users. These issues are particularly salient for ECIGs due to their increasing popularity (USDHHS, 2016). As the Surgeon General noted, "E-cigarette use among U.S. youth and young adults is now a major public health concern" (USDHHS, 2016, p. vii). Addressing this public health concern through regulation will be challenging because ECIGs are an evolving product class with great variability in nicotine content, device power, and flavors (USDHHS, 2016). These characteristics can influence user behavior including subjective effects, liquid consumption, and nicotine delivery (Hiler et al., in press; Wagener et al., 2017). Also, puffing behavior (i.e., puff topography, including puff number and duration) helps to determine the amount of nicotine delivered to the user and thus ECIG subjective effects (e.g., Hiler, et al., in press). Regulatory action intended to influence ECIG effects must account for these factors. If FDA is to understand how tobacco product regulation will influence the risks and benefits to ECIG users and tobacco cigarette smokers, it may learn much from robust scientific methods that predict the likely population-level impact of potential regulatory action. To understand the benefit of predicting regulatory impact, consider the European Union's (EU's) Tobacco Products Directive 2014/40/EU that limits ECIG liquids to <20 mg/ml nicotine to allow "for a delivery of nicotine that is comparable to the permitted dose of nicotine derived from a standard cigarette...". This directive does not account for variability in product characteristics and user behavior that work against its intent and may increase public health risk. For instance, consider device power: early ECIG models were powered at 10 W or less, but current models achieve 150 W or more (Wagener et al., 2017). Ten puffs from high power ECIGs (mean=70 W) filled with low nicotine concentration liquid (mean=4 mg/ml) can meet and sometimes exceed the nicotine delivery of a tobacco cigarette (Wagener et al., 2017).

Use of these "third generation" ECIGs is on the rise (e.g., Barrington-Trimis et al., 2017) and, relative to lower power devices, they can lead users to consume more nicotine-containing liquid (e.g., Wagener et al., 2017; Etter, 2016). In addition, based on information on e-cigarette forums, individuals are using both low and higher-nicotine concentration liquids (as high as 35 - 50 mg/ml) in their "third generation" devices.

Taken together, these results suggest that, when higher power devices are available, the intended consequences of the EU directive are unlikely to be realized and unintended consequences (more toxicants inhaled) are likely because users can buy high power devices that lead users to consume more liquid, and deliver nicotine more efficiently, even when paired with liquids <20 mg/ml nicotine. The ability to predict the consequences of regulatory action might help FDA craft policies that meet their intent while limiting unintended consequences like these. Indeed, if FDA had scientific methods that could predict these population-level outcomes in advance, these methods could be used to generate objective data to guide the development of potential regulation. Then, by the time data-guided regulations are enacted, they will have been crafted to maximize intended effects and minimize unintended consequences. Our goal is to provide these methods to FDA. To do so, we examine hypotheses related to the effects on user behavior of three potential regulatory actions: limiting nicotine concentration (described here), constraining nicotine flux (nicotine yield/unit time), and reducing flavor availability (these will be tested in other studies). We then use results from the controlled clinical lab testing described here, along with results from other studies, to generate predictions about how these potential regulatory actions might impact the population, and then test our predictions at the population level (in a separate study not described in this protocol).

### 2. \* Describe the study hypothesis and/or research questions. Use lay language whenever possible.

The purpose of this study is to determine differences in nicotine delivery, use behavior (puff topography), carbon monoxide delivery, subjective effects, and physiological effects, when cigarette smokers and experienced electronic cigarette users use an electronic cigarette with different settings (different voltage and resistance settings, which together determine power levels) and different e-liquid concentrations.

### 3. \* Describe the study's specific aims or goals. Use lay language whenever possible.

The aims of this study are to better understand how electronic cigarettes with different settings (voltage and resistance, which together determine power levels) combined with liquids of differing nicotine concentrations effect a variety of measures.

This aim involves manipulating liquid nicotine concentration and device power, testing the hypothesis that abstinence suppression, liquid consumption, and nicotine delivery will be lower as nicotine concentration is lowered, but these effects will be offset by higher power. Also, relative to smokers, ECIG users will take longer puffs, thus increasing nicotine delivery and liquid consumed.

### 4. \* Describe the scientific benefit or importance of the knowledge to be gained:

The benefits of this research are of a scientific nature, which should in the long-term benefit society at large. In particular, the use of ECIGs has become increasingly popular, especially among individuals aged 18-24. New regulations are being targeted at this age group and need to be tested in this age group before implementation. The overarching theme of the Center for the Study of Tobacco Products is to provide regulators (FDA and others) with a suite of tools that allow them to test regulations before they are implemented to determine if those regulations will have their intended consequences without causing harm (i.e., unintended consequences). If we cannot study the age group the regulations are targeting, we cannot test potential regulations effectively.

In addition, there is a lack of information about ECIGs and their effects. The results of this study will inform future work regarding the physiological and subjective effects of ECIG use in e-cigarette and cigarette smokers.

**5. \* Describe any potential for direct benefits to participants in this study:**  
None.

**6. Upload a supporting citation list if applicable:**

## Study Population

### 1. \* Provide the maximum number of individuals that

1. May participate in any study interaction or intervention (Including screening, consenting, and study activities)

AND/OR

2. You obtain any data/specimens about (regardless of identifiability)

at VCU and at other sites under the VCU IRB's oversight. See the help text for additional guidance.

300

### 2. If this is a multi-Center Project, what is the maximum anticipated number of subjects across all sites?

### 3. \* Provide justification for the sample size by explaining how you arrived at the expected number of participants and why this number is adequate for answering the research questions:

136 completers (68 cigarette smokers and 68 ECIG users) are required to achieve sufficient sample size. In order to obtain 136 completers, we may consent up to 300 individuals.

To determine sample size, we needed first to estimate effect sizes for key outcomes of subjective effect, puff topography, and plasma nicotine. Results revealed that for all within-subject analyses, 32 participants were required to achieve power >80% given a Type I error rate of 0.05. For between-subject analyses, 42 participants/group were required for plasma nicotine, 66 participants/group were required for puff duration, and 68 participants/group were required for subjective measures. Each outcome is important; thus, we are proposing 68 participants for each group in order to power for between-subject subjective effect differences at >80%, with the understanding that we may be over-powered for some measures.

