After screening and informed consent, eligible participants will enroll in this study, which is modeled on our previous work (e.g., Spindle et al., 2016; Hilier et al., 2017). A total of 136 participants (68 cigarette smokers and 68 experienced ECIG users) are needed to complete the study. Once enrolled, participants will attend the lab for six additional experimental sessions (approximately 4 hours each) where they use an "open system" ECIG (Kanger Sub Box Mini) set to either 15 watts or 30 watts, which will contain either 10mg, 15 mg, or 30 mg nicotine-containing liquid. The design of this study is within-subjects, thus, all participants will complete six sessions that differ by the combination of watts and liquid concentration. Sessions will be ordered by Latin-square. The sessions will occur no more than 2 days per week and will be separated by at least 48 hours. The approximate total time that participants will be in the laboratory is 24.5 hours (30 minutes for screening and 24 hours for sessions). This does not include the 12 hours before each session that we ask participants to abstain from and nicotine/tobacco containing products.

During each session, participants will first complete a 10-puff product use bout, and then a 90-minute ad lib product use bout. Sessions will be preceded by 12 hours tobacco/nicotine abstinence (to measure the extent to which each device/liquid combination suppresses nicotine/tobacco abstinence symptoms), and session order will be ordered by Latin-square. In all sessions, participants will use topography-measurement equipment (a mouthpiece attached to the ECIG that is attached to a computer via tubing; the participant then puffs on the mouthpiece). Other outcomes include plasma nicotine, cardiovascular response, carbon monoxide level, and subjective effects (direct effects of the ECIG and nicotine, abstinence symptoms).

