More specifically, upon arrival at the laboratory for each session, participants' breath CO will be measured to ensure compliance with the overnight abstinence criteria (i.e. CO < or equal to 10 ppm for cigarette smokers, see Breland et al., 2006, or < or equal to 7 ppm for ECIG users). In addition, participants will be asked questions about symptoms experienced since the last visit. Once deemed abstinent, participants will begin a 1-hour waiting period. During this time, participants cannot eat or use their cell phones, although water, movies, and/or magazines will be provided. We have recently instituted this 1-hour waiting period in other studies, because we find, after looking at plasma nicotine levels which are analyzed months after participants complete studies, that some participants do not comply with the 12-hour nicotine/tobacco abstinence requirement. Adding this 1-hour waiting period ensures that all participants are abstinent for at least one hour before the session begins. After the 1-hour waiting period, an IV catheter will be inserted into a forearm vein of the participant, physiological monitoring equipment will be attached (arm blood pressure cuff, pulse oximotor placed on finger), and a 30-minute rest period will begin. This rest period allows us to measure resting heart rate and blood pressure immediately before product administration. A detailed timeline of the sessions is described below. Please note that because catheter insertion can be difficult, we will attempt to insert a catheter no more than three times in one day, and if all three attempts are unsuccessful, the session will be discontinued, with payment as outlined in the consent and compensation section.

The subjective questionnaires administered at each time point are as follows: Direct Effects of Vaping Questionnaire, Direct Effects of Nicotine Questionnaire, Hughes-Hatsukami Questionnaire, and the General Labeled Magnitude Scale. All of these questionnaires will be administered via computer or RedCap with the exception of the General Labeled Magnitude Scale, which may be administered via paper and pen, or via RedCap. At the end of each session, participants will also be asked one additional question: "Do you believe that you received nicotine today?" (Participants' answer will be entered into RedCap).

Experimental session timeline (times approximate):

Participant arrives, CO test to confirm tobacco abstinence, additional questions about symptoms asked  

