## Compensation

1. \* Describe any compensation that will be provided including:

1. total monetary amount
2. type (e.g., gift card, cash, check, merchandise, drawing, extra class credit)
3. how it will be disbursed

Participants will be paid \$10 after the in-person screening visit. Participants will receive \$50 after completing the first session, \$75 after completing the second session, \$100 after completing the third, fourth sessions, \$150 after completing the fifth session, and \$175 after completing the sixth session. Thus, the total amount participants could earn for the entire study is \$660. If a participant chooses to leave the study early, he or she will keep the amount earned up to that point. In addition, if a session must be discontinued for reasons beyond the control of the participant, the participant will be paid for the time spent complying with study conditions before the session began (\$15) and also the time spent in the laboratory (\$15/hour). All payments will be in the form of cash.

This amount was chosen because of the number of hours that participants are asked to be in the laboratory (24 hours for sessions), which does not include the 12 hours that we ask them to abstain from tobacco products before they come to the lab for each session. In addition, we will insert an in-dwelling catheter for each session. With the time involved in the laboratory, time abstaining before coming to the laboratory (which can be very unpleasant) and possible discomfort from the catheter, we feel that the compensation is appropriate, and not coercive--in order to receive payment, participants have to do quite a bit.

In addition, there may be rare instances in which the equipment we use malfunctions during a session. If this happens, we may stop the session and ask the participant to return on another day to repeat that session. In these instances, if the equipment malfunctions in the first half of the session, we will pay participants half of the money they would have earned in that session. If the equipment malfunction occurs in the second half of the session, we will pay the participant the full amount for that session.

2. If compensation will be pro-rated, explain the payment schedule.

3. \* Will Social Security Numbers be collected for compensation purposes only?

- Yes
- No

[Print](#)

[Close](#)

View: SF2 - Consent Process

HM20012738 - [name]  

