4. Where appropriate, discuss provisions for ensuring necessary medical, professional, or psychological intervention in the event of adverse events to the subjects:  
Individuals whose heart rate and/or BP levels remain elevated will be monitored continually by the nurse and if, necessary, emergency responders will be notified. Emergency medical converge will be available via the emergency room that is 1.5 miles from the CBPL/CSTP.

5. \* Describe criteria for when the investigator would withdraw an individual participant from the study; such as safety or toxicity concerns, emotional distress, inability to comply with the protocol, etc.:  
Participants may be withdrawn from the study if the PI or study nurse has any safety concerns (such as continuous high blood pressure or heart rate) during sessions, or if an intravenous catheter cannot be successfully inserted.

Additionally, participants can be withdrawn if they are unable to follow protocol guidelines and/or are unable to keep their scheduled session appointments.

6. \* Summarize any pre-specified criteria that would trigger the investigator/sponsor/monitoring committee to stop or change the study protocol due to safety concerns:  
At this time we do not have a pre-specified criteria for stopping or changing the study protocol due to safety concerns.

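### Does recruiting to 136 completers ask for more than the plan's own power figures need?

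*Combined protocol and SAP*

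**What the plan says.** Study Population, item 3 sets the target: "136 completers (68 cigarette smokers and 68 ECIG users) are required to achieve sufficient sample size". The supporting results follow. Within subjects, "for all within-subject analyses, 32 participants were required to achieve power >80% given a Type I error rate of 0.05". Between subjects, "42 participants/group were required for plasma nicotine, 66 participants/group were required for puff duration, and 68 participants/group were required for subjective measures". The largest figure, 68, is adopted for both groups, and the plan accepts that some measures will then have more power than they need.

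Study Procedures, item 6 repeats the target ("A total of 136 participants (68 cigarette smokers and 68 experienced ECIG users) are needed to complete the study") and describes the design: "all participants will complete six sessions that differ by the combination of watts and liquid concentration".

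Other sections foresee incomplete participation. In Study Procedures, item 6, up to three catheter attempts are allowed and "if all three attempts are unsuccessful, the session will be discontinued". Risks, item 5 lists grounds for withdrawal, among them "or if an intravenous catheter cannot be successfully inserted". Compensation, item 1 covers early leavers: "If a participant chooses to leave the study early, he or she will keep the amount earned up to that point".

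No effect size, drop-out rate, within-person correlation, analysis model, analysis set or rule for missing sessions is given.

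**The concern.** The unit changes between the calculation and the target. The calculation counts participants; the target counts completers. Only the within-subject contrasts inherently need several sessions from one person, and they need 32. The number that fixes the total, 68 per group, is for a comparison between groups, to which someone with three sessions still contributes.

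There would then be a cost either way. If incomplete participants were dropped, usable questionnaire and puff data would be lost on the outcomes that set the sample size, and the non-randomised group comparison could be biased if completion differed by group for reasons tied to the outcome. If they were kept, recruiting to 136 completers would enrol more people than needed, each facing up to six catheterised sessions and 168 ml of blood (Sample Collection Details, item 5).

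**Working it through.** **The plan's figures.** 2 × 68 = 136 is exact. The figures 32, 42, 66 and 68 cannot be recomputed, because no effect sizes are given. They can be turned back into standardised differences. For a two-sided two-sample t-test at 0.05 with 80% power, 42, 66 and 68 per group correspond to d = 0.619, 0.491 and 0.484. The normal formula d = (1.960 + 0.842) × √(2/n) gives 0.480 at n = 68. These values are unremarkable. They do not show whether the test used one session per person, one condition, or an average over six.

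**Assumptions.** Completion c = 90, 80 or 70% of starters; constant drop-out over the five gaps between sessions; within-person correlation r = 0.3 to 0.7; drop-out unrelated to response.

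**Information from a partial participant.** For the group difference pooled over conditions, k sessions relative to six carry

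(r + (1 − r)/6) / (r + (1 − r)/k).

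At r = 0.5 this is 0.583, 0.778, 0.875, 0.933 and 0.972 for k = 1 to 5. For k = 1 it is 0.417 at r = 0.3 and 0.750 at r = 0.7.

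**Worked case, c = 0.8 and r = 0.5.** The chance of continuing at each gap is 0.8^(1/5) = 0.9564. The shares stopping after sessions 1 to 5 are 0.0436, 0.0417, 0.0399, 0.0382 and 0.0365, and 0.8 complete. Mean information per starter = 0.0436 × 0.583 + 0.0417 × 0.778 + 0.0399 × 0.875 + 0.0382 × 0.933 + 0.0365 × 0.972 + 0.8 = 0.964. Reaching 68 completers takes 68/0.8 = 85.0 starters per group, worth 85.0 × 0.964 = 81.9 completers. Power at d = 0.484 is 86.8%.

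**All cases (ranges run from r = 0.3 to r = 0.7).** Completers-only power with 68 per group is 80% throughout.

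| Completion | Starters per group for 68 completers | Information per starter | Worth in completers | Power, all sessions kept | 68 starters: worth in completers | 68 starters: power |
|---|---|---|---|---|---|---|
| 90% | 75.6 | 0.973–0.990 | 73.5–74.8 | 83.0–83.7% | 66.1–67.3 | 78.9–79.6% |
| 80% | 85.0 | 0.944–0.980 | 80.3–83.3 | 86.1–87.4% | 64.2–66.6 | 77.7–79.2% |
| 70% | 97.1 | 0.914–0.969 | 88.8–94.1 | 89.4–91.0% | 62.2–65.9 | 76.3–78.7% |

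The last two columns test the rule of counting anyone with at least one session. If 68 presumes six-session data, that rule falls below 80% in every case. A one-session participant also adds essentially nothing to the 32 needed within subjects.

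**A stricter alternative.** Suppose recruitment stopped once each of the six conditions had 68 people per group. Simulated recruitment (4,000 runs) gives mean totals of 146.4 / 156.5 / 167.6 at 90 / 80 / 70% completion, against 136/c = 151.1 / 170.0 / 194.3 for the completer target. The saving is about 5 / 14 / 27 people. About 66 / 63 / 59 completers per group would remain, instead of 68.

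**The catheter example.** A failed insertion seems to lose only blood, and plasma nicotine needs just 42 per group. The session timeline in Study Procedures, item 6 shows otherwise. The catheter is placed at 1 h 00, the first questionnaires come at 1 h 30 and the first puffs at 1 h 35. A session ended by failed insertion has produced no questionnaire or puff data, so nothing on those outcomes can be recovered from it.

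**The case for a change.** The strongest case for a change is that the plan gives no reason for turning 68 participants into 68 completers, foresees incomplete participation, and is silent on the data of those who leave. Extra enrolment burdens people who have no direct benefit. The per-condition count also survives the test that the looser rule fails. Under the same assumptions it secures 68 per group for any single-condition contrast, keeps power for the pooled group difference at about 82–85% (simulated at correlation 0.3–0.5), and leaves far more than 32 completers.

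The silence about model and missing sessions is real. But a completer count is a recruitment target, not an analysis set, and it does not imply that partial data are thrown away. The description of everyone completing six sessions states the within-subject design; provisions for early leavers do not contradict it.

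The per-condition count is workable but not clearly better. The central hypothesis (Background, item 3) is that higher power offsets lower nicotine concentration, which is a within-person question, alongside group differences. Group-by-condition effects were not sized, and people with all six conditions inform them best. Giving up some completers to save an assumed 5 to 27 enrolments is a judgement the investigator may reasonably make either way.

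**Conclusion.** No change is needed. That 136 completers exceed what the plan's figures require is unproven, because the sessions per person and the contrast behind 68 are not stated. Recruiting as written reaches the stated power with complete data, with 68 completers in each group against 32 for within-subject analyses. The target is a defensible margin.

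The unstated handling of incomplete participants is a reporting gap that an analyst would sensibly fill with a mixed model on all recorded sessions, showing completers alone as a check. Compared with discarding partial data, which the plan does not say it will do, that raises power for the pooled group difference from 80% to about 83–84, 86–87 or 89–91% at 90, 80 or 70% completion. It assumes that drop-out depends only on recorded data. Any bias from analysing completers alone cannot be estimated from the documents.

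All sizes here rest on assumed completion, with the power figures also resting on assumed correlation. At 90% completion the gain is about 3 to 4 percentage points of power, or 5 fewer people under the per-condition count.

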0 Hr 00 1-hour waiting period  
1 Hr 00 Hr Insert venous catheter, attach physio equipment, 30-minute rest period begins  
1 Hr 30 Subjective effects questionnaires, baseline blood sample 1, CO test  
1 Hr 35 10 puffs from ECIG (30s inter-puff interval)  
1 Hr 40 Blood sample 2 (immediately after last puff), subjective effects questionnaires, CO test  
2 Hr 00 Blood sample 3, subjective effects questionnaires, CO test, ad lib use period begins  
3 Hr 30 Ad lib use period ends, blood sample 4, subjective effects questionnaires, CO test  
Participant asked last question, "Do you believe that you received nicotine today?"  
Remove Catheter  
Stop Physio Monitoring  
Payment  
Release

7. \* The IRB only reviews research activities, so indicate which of the study activities are:

- Being performed exclusively for research purposes (i.e. they would not otherwise be done apart from this study) VERSUS.
  - Alterations of routine activities/procedures (e.g. the study is altering the timing, frequency, method, location, amount, etc.) VERSUS.
  - Being done for other purposes and whose data/results will be used secondarily in the study (e.g. standard medical or psychological tests, routine education practices, quality improvement initiatives, etc.).
- All procedures are performed exclusively for research purposes.

8. If applicable, describe alternatives (research or non-research) that are available to potential participants if they choose not to participate in this study:

9. Upload any supporting tables or documents (e.g. protocol documents, figures/tables, data collection forms, study communications/reminders):

Upload ALL instruments/guides that will be used or that participants will experience (i.e. see, hear, complete), including measures, scripts/questions to guide interviews, surveys, questionnaires, observational guides, etc.:

Upload ALL recruitment and screening materials, including such as ads, flyers, telephone or in-person scripts, letters, email invitations, TelegRAM announcements, and postcard reminders, screening scripts, screening forms, and screening measures:

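### Does the between-group sample size need changing because the subjective measure behind 68 per group is unnamed, liquid consumed is unsized and no primary outcome is stated?

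*Combined protocol and SAP*

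**What the plan says.** Study Population, item 3, starts from estimated effect sizes for subjective effects, puff topography and plasma nicotine. For the within-subject analyses, "32 participants were required to achieve power >80% given a Type I error rate of 0.05". Between groups, plasma nicotine needs 42 per group, and "66 participants/group were required for puff duration, and 68 participants/group were required for subjective measures". The largest figure is adopted ("Each outcome is important; thus, we are proposing 68 participants for each group in order to power for between-subject subjective effect differences"), "with the understanding that we may be over-powered for some measures". The total is 136 completers, with up to 300 people consented.

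The aims (Background, item 3, repeated in Study Procedures, item 2) carry the group hypothesis: "relative to smokers, ECIG users will take longer puffs, thus increasing nicotine delivery and liquid consumed". The research question (Background, item 2, repeated in Study Procedures, item 1) is broader. It covers nicotine delivery, puff topography, carbon monoxide, subjective effects and physiological effects in both user groups.

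Study Procedures, item 6, says topography is recorded in every session and adds: "Other outcomes include plasma nicotine, cardiovascular response, carbon monoxide level, and subjective effects". It then introduces four instruments ("The subjective questionnaires administered at each time point are as follows"). The session timeline gives them at baseline and at three times after product use begins, the last being "Ad lib use period ends, blood sample 4, subjective effects questionnaires, CO test". There are six sessions per participant.

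**The concern.** Three things look wrong on a first reading.

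- **The outcome that fixes the sample size cannot be identified.** With four questionnaires, three times after use begins and six sessions, many scores could be the one behind 68. If the score were picked after the data were seen, the false-positive rate would exceed 5%.
- **The sized outcomes and the group hypothesis differ.** Subjective effects set the size but are not in the group hypothesis. Liquid consumed is in the hypothesis but has no group size, and neither the outcome list nor the timeline mentions it.
- **No primary group contrast or multiplicity position is stated.** The 0.05 is written in the within-subject sentence, so its use between groups is inferred.

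At stake would be a sample size that nobody can check, a hypothesised outcome of unknown power, and group results that could be read either as separate tests or as one joint claim.

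**Working it through.** **Inputs from the plan:** 42, 66 and 68 per group; power above 80%; Type I error rate 0.05 (stated for the within-subject analyses); 136 completers; 300 consented.

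**Assumptions, not in the plan:** two-sided 0.05, a two-sample t-test, and power of exactly 80% at each stated size. No effect size, SD, sidedness or test is given, so 68 cannot be reproduced forwards. It can only be solved backwards.

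**1. Implied standardised differences.** In the normal approximation, d = (1.960 + 0.842) × √(2/n).

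| Outcome | n per group | d (normal) | d (t-based) | Power at 68 (t-based) |
|---|---|---|---|---|
| Plasma nicotine | 42 | 0.611 | 0.619 | 94.8% |
| Puff duration | 66 | 0.488 | 0.491 | 81.2% |
| Subjective measures | 68 | 0.481 | 0.484 | 80.0% |

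The last column is consistent with the plan's own remark about over-powering. Nothing here shows 68 to be wrong.

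**2. Match to the hypothesis.** The group hypothesis has three parts. Longer puffs are sized at 66. Nicotine delivery is sized through plasma nicotine at 42. Only liquid consumed is unsized. Its power at 68 per group depends on an assumed d: 41% at 0.3, 64% at 0.4 and 80% at 0.484. The subjective outcome is outside the directional hypothesis but inside the research question, and the form asks whether the number is adequate for the research questions.

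**3. Score selection.** Suppose there is no true subjective difference and an analyst reports whichever score reaches p < 0.05. With four independent scores the chance of a false finding is 1 − 0.95⁴ = 18.5%; at correlation 0.8 it is about 12% (simulated). With twelve scores (four questionnaires at three times) it is 1 − 0.95¹² = 46% under independence and about 19% at a common correlation of 0.8. The same people answer the same questionnaire repeatedly, so independence is not credible. With correlations of 0.7 to 0.8 within a questionnaire and 0.3 to 0.5 between questionnaires, simulation gives roughly 27% to 34%. All of these require selective reporting and an assumed number of scores. The plan specifies neither.

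**4. Unadjusted tests of the three sized outcomes.** If all three nulls are true, the chance of any false finding is 1 − 0.95³ = 14.3% under independence and about 10% at correlation 0.8.

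**5. What a family-wise rule would cost.** For the subjective measure at 0.05/3, power at 68 per group is 65%, and 80% needs 91 per group. That is 2 × 91 = 182 completers, or 182/300 = 61% of the consent ceiling against 136/300 = 45% now. With Holm and all three effects real, puff duration and the subjective measure have 75% to 78% power at 68, and about 76 per group restores 80%. Testing each outcome at 0.05, or naming one sized outcome as primary at 0.05, leaves 68 unchanged.

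**The case for a change.** The strongest case for acting is that the same sentence names puff duration exactly, so the subjective score could have been named too. The form asks for enough detail to replicate the methods and records no separate protocol, and the document contains no analysis section that fills the gap. The study's results are also meant to feed predictions about regulation, so a score chosen after the fact would carry forward. Naming it would cost a sentence.

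The factual part stands: the score, time point, session handling and effect size behind 68 are not recorded, and no measurement step is described for liquid consumed.

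The rest is weaker. The plural wording may mean that 68 covers several subjective measures rather than one hidden score. Naming the score alone would not make 68 checkable, because the effect size, SD, sidedness and test would still be missing. The outcome list is worded as non-exhaustive, and the timeline also omits topography, which the text says is recorded in every session. Silence there is therefore poor evidence that liquid consumed goes unmeasured. On multiplicity, taking the largest of several per-outcome sizes and accepting excess power elsewhere is a recognisable per-outcome design. The resulting predictions are to be tested in a separate population-level study, which makes strict family-wise control here a choice rather than a necessity.

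**Conclusion.** No change to the plan is needed. The gap is missing documentation, and no figure, test or decision in the plan is shown to be wrong. If the stated sizes just reach 80% in two-sided 0.05 t-tests, all three sized outcomes have at least 80% power at 68 per group, including two of the three hypothesised group outcomes. The subjective measures lie within the research question, so sizing on them is not a mismatch.

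The per-outcome reading at 0.05 is the natural one, although its use between groups is inferred. It carries a 10% to 14% chance of at least one false group finding if all three nulls hold. That is a fair trade-off for a laboratory study that treats several outcomes as important. Family-wise control would cost power or completers on effects that are themselves only back-solved. The higher score-selection rates illustrate what selective reporting could do and are not a property of this plan.

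Liquid consumed is the one hypothesised group outcome without stated power (41% to 80% for assumed d of 0.3 to 0.484). Analysts can report it with its estimate and interval, and can state the subjective score and per-outcome testing when they document the analysis. Neither step alters the design, the 136 completers or the planned comparisons.
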